Project code	EpidProtect-21
Study title	Exhaustive, cross-sectional, non-interventional, multicenter retrospective epidemiological study of the COVID-2019 incidence and prevention methods of SARS, including COVID-2019, among staff of participating organizations.
Version of Synopsis	0.2, 15.02.2021.
Justification of study	
Coronaviruses are a large family of viruses that might cause illness in animals or humans. SARS-CoV-2 is an enveloped, single-stranded RNA virus of the β genus. It can cause respiratory illness named COVID-19, the severity of which varies from asymptomatic to severe, and which can lead to the patient's death or long-term consequences (so-called post-COVID syndrome). The virus has spread globally and been declared a Public Health Emergency of International Concern by WHO in January 30, 2020.
 
The first case of COVID-19 in Ukraine was detected in early March, 2020. 1273475 cases of the disease have been registered in Ukraine as at February 15, 2021.
 
Quarantine restrictions and other anti-epidemic measures established in Ukraine and their results are the subject of wide debate.
 
Own anti-epidemic measures, in addition to those established by the Government, have also been implemented by numerous representatives of the public sector, non-governmental organizations and business.
 
The company management of the participating organizations decided to provide their staff with prophylactic tools and recommendations for COVID-19 prevention.
 
The study aims to identify the incidence, characteristics of cases and their relationship with the preventive measures used.

Study design	Exhaustive, cross-sectional, non-interventional, multicenter retrospective epidemiological study, case study.
Number of subjects	3443 subjects.

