Location of study conduct	
Each subject will participate in the study in the participating organization by which the subject is employed:
 
• SI National Institute of Phthisiology and Pulmonology named after F.G. Yanovsky.• Yuria-Pharm LLC.• Infuzia PJSC.• Institute Hyalual LLC.• Medical Center M.T.K. LLC.• InterChem SLC.• Diatom LLC. 
For the study the following facilities will be organized at each participating organization:
 
• Specially designated locations for material collection and conduction of rapid ELISA tests for the antibodies to COVID-2019.• Specially designated computerized places for questionnaires with assigned staff who organize the order and accuracy of the questionnaire conduct.
Duration of data collection	3 months.
Purpose of the study	To determine the relationship between the systematic use of prophylactics to prevent SARS, including COVID-2019, and the risks of incidence and serious complications of COVID-2019 among staff of participating organizations.
Study objectives	
• To investigate the incidence of COVID-2019 cases in participating organizations.• To investigate the severity of the COVID-2019 cases in participating organizations.• To explore the prevention methods used by staff members.• To determine the relationship between the used prevention methods and incidence of COVID-2019 among staff of participating organizations.

	
• To determine the relationship between the presence of comorbidities, such as bronchial asthma and COPD, and the incidence/severity of COVID-2019.• To determine the relationship between the COVID-2019 case and the course of comorbidities, such as bronchial asthma and chronic obstructive pulmonary disease (COPD).• To identify the relationship between different strategies and combinations of drugs used for prophylactics at any time from March 2020 and the risk of having a COVID-2019 case.• To identify the relationship between different strategies and combinations of drugs used for prophylactics at any time from March 2020 and the risk of having a severe COVID-2019 case.• To identify the relationship between different strategies and combinations of drugs used for prophylactics at any time from March 2020 and the risk of hospitalization of persons who had at least one COVID-2019 case.

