Study endpoints	
• The incidence of COVID-2019 cases in participating organizations.• The severity of the COVID-2019 cases in participating organizations.• Prevention methods of SARS, including COVID-2019, which were used by subject who had at least one COVID-2019 case.

	
Prevention methods of SARS, including COVID-2019, which were used by subject who did not have any COVID-2019 case.Relationship between the used prevention methods and incidence of COVID-2019 among staff of participating organizations.Relationship between the presence of comorbidities, such as bronchial asthma and COPD, and the incidence/severity of COVID-2019 case.Relationship between the COVID-2019 case and the course of comorbidities, such as bronchial asthma and chronic obstructive pulmonary disease (COPD).Relationship between different strategies and combinations of drugs used for prophylactics at any time from March 2020 and the risk of having a COVID-2019 case.Relationship between different strategies and combinations of drugs used for prophylactics at any time from March 2020 and the risk of having a severe COVID-2019 case.Relationship between different strategies and combinations of drugs used for prophylactics at any time from March 2020 and the risk of hospitalization of subjects who had at least one COVID-2019 case.
Study variables	
Demographic characteristics: age, gender.Anthropometric characteristics: body weight, height.Blood group.Number of people in the household.Lifestyle: the presence of bad habits, physical activity, diet.Medical history: comorbidities, their treatment.Prevention methods of SARS, including COVID-2019, currently used by the subject.Number of COVID-2019 cases, which subject had.Characteristics of the disease case, its treatment.

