Study limitations	
Persons, who were employed by one of the participating organizations from March 1, 2020, but who do not have employment relations with the participating organizations during the study period or persons who are on maternity leave, will not be included in the study.
 
Another study limitation is duration of data collection (due to long-term data collection there is a difference in the duration of action of the exposure factor).
 
The retrospective study design has limitations on the completeness and accuracy of the data provided by the study subjects.
 
There may be difficulties in filling in the missing data.
 
Certain relationships can be difficult to describe.
 
The direction of the relationship cannot be determined for all relationships (there may be an inverse relationship).
 
Potential data distortion may be due to the subject selection; use of an electronic data collection system; possible low computer literacy of some subjects; lack of data verification and query generation.
 
The completeness and correctness of the description of available medical documentation for fatal cases of COVID-2019 depends on the amount of information provided and its quality. Conclusions from it cannot be extended to other population members.

-------------------	---

Statistical analysis plan

In the context of this data analysis, all the main steps from the primary data to the results of the study will be described separately in the Statistical Analysis Plan.

This study is not intended to accept or reject pre-defined hypotheses, thus statistical analysis will mainly be descriptive.

All types of analysis will be done for the entire available study population with available data.

If there is a sufficient amount of data in the subpopulations, a separate statistical analysis will be performed.

No conditional calculation methods will be applied to the missed values.

The statistical generalization will consist of frequency tables of categorical variables (number, %).

For metric variables, descriptive statistics (number of subjects with available observations, number of missed values, mean, standard deviation, median, 25th and 75th percentiles, minimum and maximum) will be presented in tabular form.

Statistical conclusions will be used to assess the potential relationship between the identified variables and the incidence / severity of COVID-2019.

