The relationship between the subject's characteristics and the variables of interest will be assessed using a one-dimensional and multidimensional (polynomial) logistic regression model for variables, which have no more than 20% omitted data.

The final model will be selected with a view to minimizing the Akaike information criterion value.

2×2 tables, χ^2 -square were used for calculations of odds ratios.

Rough odds ratios and adjusted odds ratios with corresponding 95% confidence intervals and p-values will be generated and presented for both one-dimensional and multidimensional logistics models.

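### Employer is known for every subject, but the outlined prophylaxis odds ratios are neither stratified by nor adjusted for it

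*Combined protocol and SAP*

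**What the plan says.** The Purpose of the study section sets the main aim: "To determine the relationship between the systematic use of prophylactics to prevent SARS, including COVID-2019, and the risks of incidence" and serious complications. Prophylaxis is not randomised. The Justification of study section reports that "The company management of the participating organizations decided to provide their staff with prophylactic tools and recommendations for COVID-19 prevention".

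Employer is fixed by design. Under Location of study conduct, "Each subject will participate in the study in the participating organization by which the subject is employed", and seven organisations are listed. Employment by one of them is also an inclusion criterion.

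The Study variables section begins with "Demographic characteristics: age, gender". It goes on to body measurements, blood group, household size, lifestyle, medical history, prevention methods, case history and costs. Neither employer nor any occupational variable appears.

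The Statistical analysis plan section pools all subjects with data and calculates odds ratios from 2×2 tables. It adds that associations with subject characteristics "will be assessed using a one-dimensional and multidimensional (polynomial) logistic regression model", with the final model being the one with the lowest AIC. No covariate is forced in. The output is definite: "Rough odds ratios and adjusted odds ratios with corresponding 95% confidence intervals and p-values will be generated and presented". Unnamed subpopulations may be analysed separately if the data allow. The section also says that "This study is not intended to accept or reject pre-defined hypotheses, thus statistical analysis will mainly be descriptive", and that "all the main steps from the primary data to the results of the study will be described separately in the Statistical Analysis Plan". That separate plan is not in the supplied text.

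**The concern.** By the study's own rationale, one driver of exposure sits at employer level, because management supplied the prophylactics and the advice. Infection risk may also vary by workplace: judged by name only, the list mixes medical institutions with companies. If both uptake and risk differ between organisations, a pooled 2×2 odds ratio mixes any effect of the prophylactic with the difference between workplaces. It could show benefit or harm where neither exists.

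The multivariable model would remove this only so far as the listed covariates explain the differences between organisations, and none of them describes work. Separate subpopulation analyses, even if done by organisation, would not adjust the pooled odds ratio. Since the outlined outputs do not specify uptake or incidence by organisation, a reader could not tell whether the problem is present.

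The documents do not say that supply, uptake or risk differed, so the concern is conditional.

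**Working it through.** **Inputs.** 3443 subjects (Number of subjects) and seven organisations (Location of study conduct). The documents give no incidence or uptake figures for the organisations, and a sample size calculation is declared not applicable, so there is no planned figure to reproduce. Every rate and the split into medical and other settings below are assumptions.

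**Model.** Two groups: n1 in medical settings and n2 = 3443 − n1 elsewhere, with uptake u1, u2 and incidence p1, p2. Incidence is the same for users and non-users within each group, so the true odds ratio (OR) is 1. Pooled expected counts:

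- cases among users: a = n1·u1·p1 + n2·u2·p2
- non-cases among users: b = n1·u1·(1−p1) + n2·u2·(1−p2)
- c and d are the same for non-users, with 1−u in place of u
- OR = ad/(bc); SE of ln OR = √(1/a + 1/b + 1/c + 1/d); 95% CI = exp(ln OR ± 1.96·SE)

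**One case in full.** n1 = 1000, n2 = 2443, incidence 25% vs 18%, uptake 40% vs 60%.

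- Users: 400 + 1465.8 = 1865.8, with 100 + 263.8 = 363.8 cases (19.50%)
- Non-users: 600 + 977.2 = 1577.2, with 150 + 175.9 = 325.9 cases (20.66%)
- OR = (363.8 × 1251.3)/(1502.0 × 325.9) = 0.93; SE = 0.0853; CI 0.79–1.10

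**All six cases** (medical vs other):

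| n1 | Incidence | Uptake | Crude OR (95% CI) | Mantel-Haenszel OR | SE ratio, MH to crude |
|---|---|---|---|---|---|
| 1000 | 25% vs 18% | 40% vs 60% | 0.93 (0.79–1.10) | 1.00 | 1.022 |
| 1000 | 30% vs 15% | 40% vs 60% | 0.85 (0.72–1.01) | 1.00 | 1.035 |
| 1000 | 35% vs 15% | 30% vs 70% | 0.67 (0.56–0.79) | 1.00 | 1.114 |
| 500 | 25% vs 18% | 40% vs 60% | 0.96 (0.80–1.13) | 1.00 | 1.014 |
| 500 | 30% vs 15% | 40% vs 60% | 0.90 (0.75–1.07) | 1.00 | 1.025 |
| 500 | 35% vs 15% | 30% vs 70% | 0.75 (0.63–0.90) | 1.00 | 1.086 |

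Four of the six intervals include 1. Reversing uptake with n1 = 1000 gives 1.08 (0.91–1.27), 1.17 (0.99–1.39) and 1.50 (1.27–1.77). With incidence or uptake equal across groups, the crude OR is exactly 1.00.

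**Does covariate adjustment help?** Two bounding cases:

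- The listed covariates remove half of the log-odds gap in incidence (25%/18% becomes 23.1%/19.6%). The OR is 0.97, 0.93, 0.82 (n1 = 1000) and 0.98, 0.95, 0.88 (n1 = 500). Only 0.82 (0.70–0.97) excludes 1.
- A covariate's mean differs by 0.5 to 1 SD between settings but it has no effect of its own. A large-sample logistic fit with organisation omitted gives 0.93–0.94, 0.86–0.88 and 0.68–0.71 (n1 = 1000), so little is removed. Adding organisation gives 1.00.

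**What adjustment costs.** With p = n1/3443 and mean uptake u, the between-setting share of exposure variance is p(1−p)(u1−u2)²/[u(1−u)]. For n1 = 1000 and uptake 40% vs 60%: p = 0.290, u = 0.542, share = 0.290 × 0.710 × 0.04/(0.542 × 0.458) = 0.033. For 30% vs 70% it is 0.136. With n1 = 500 the two shares are 0.020 and 0.086. For uptake 10% vs 90% (n1 = 1000) it is 0.594, and intervals widen by 1/√(1−0.594) = 1.57.

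**Sparse outcomes.** At 20% incidence there are 0.20 × 3443 ≈ 689 cases. In 20,000 simulated studies, the chance that at least one of seven organisations has no hospitalised case is:

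- 3% of cases hospitalised: 31% (equal sizes) or 71% (sizes 30, 25, 15, 10, 10, 6, 4%)
- 5% of cases hospitalised: 5% or 39%

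A closed-form check with case counts fixed agrees within about 2 points.

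**The case against.** The strongest reply is that this rests on silence in an outline. The text is a synopsis that defers the detail and names no model covariate, not even age or gender. Subject characteristics could include employer, and the incidence objective can be read as calling for results by organisation. The joint decision to supply prophylactics fits a common policy at least as well as differing ones. The illustrations rest on assumed rates, and most intervals include 1.

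All of that stands as a limit on weight. It does not remove the point: age and gender are at least on the variable list, whereas employer is not, although it is held for everyone.

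A second reply is that AIC would usually keep organisation once it is a candidate. In the six scenarios the expected likelihood-ratio statistic for setting alone is 21, 96, 161 (n1 = 1000) and 13, 60, 101 (n1 = 500), against an AIC penalty of 2 × 6 = 12 for six indicators. That is largely right, but it requires organisation to be a candidate, which nothing provides. At 13 against 12 it is close, and AIC does not reach the 2×2 tables.

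A third reply is that within-organisation estimates discard employer-driven exposure differences and leave self-selection and job role unadjusted, so they are not clearly less biased. This stands, and it is the reason to show both estimates rather than replace one.

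The descriptive aim does not settle the matter. A confounded odds ratio with a confidence interval and p-value can mislead without any formal hypothesis.

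**Conclusion.** The concern holds in its conditional form. Employer is known for every subject, is absent from an otherwise explicit variable list, and has no place in the pooled tables or models as outlined. If uptake and risk both differ by organisation, the crude odds ratios are confounded, and the adjusted ones are too so far as the listed covariates fail to explain those differences.

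The size cannot be derived from the documents. Modest assumed differences move a null odds ratio by a few percent. Only the largest assumed differences (incidence 35% vs 15%, uptake 30% vs 70%) give crude intervals that exclude 1. The weight is minor to moderate: the main aim is exposed and the remedy uses data already held. Confidence is medium, because the separate plan could already cover it.

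**What to change.** 1. Add employing organisation to the study variables.
2. Tabulate uptake of each prophylactic and COVID-2019 incidence by organisation. This alone shows whether the problem is plausible.
3. Report Mantel-Haenszel odds ratios stratified by organisation beside the planned crude ones.
4. Present the multivariable incidence model with organisation retained as a fixed effect (6 df) beside the AIC-selected model, not in place of it.
5. For severe cases and for hospitalisation among cases, use a stratified, conditional or penalised model, or group the organisations.
6. State that a measure nearly uniform within organisations cannot be separated from organisation, and report it descriptively.

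If the separate plan already does this, a cross-reference in the synopsis is enough.

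The cost is some wording and one variable already held. Intervals widen by 1–11% in the six scenarios, and by 2–9% for seven organisations whose uptake has an SD of 0.10–0.20. The loss becomes serious only if uptake is nearly all-or-none by employer (about 57% wider at 10% vs 90%), which step 6 covers.

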	
Prevention methods of SARS, including COVID-2019, which were used by subject who had at least one COVID-2019 case.Prevention methods of SARS, including COVID-2019, which were used by subject who did not have any COVID-2019 case.Amount of costs spent on prevention and treatment of SARS, including COVID-2019.Relationship between different strategies and combinations of drugs used for prophylactics at any time from March 2020 and the risk of having a COVID-2019 case.Relationship between different strategies and combinations of drugs used for prophylactics at any time from March 2020 and the risk of having a severe COVID-2019 case.Relationship between different strategies and combinations of drugs used for prophylactics at any time from March 2020 and the risk of hospitalization of subjects who had at least one COVID-2019 case.
Inclusion criteria	Subjects who meet all the inclusion criteria will be included in the study: 
The subject gave the consent to participate in the study and signed the consent to processing of personal data.The subject aged 18 years and older.The subject is employed by one of the participating organizations.
Exclusion/withdrawal criteria	The nature of the study does not provide for withdrawal criteria. The subject may not be included in the study due to non-compliance with the inclusion criteria or due to force majeure.
Calculation of sample size	Not applicable as it is exhaustive study. Participating organizations undertake to organize the involvement in the study of at least 95% of persons employed by participating organizations.

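### The hospitalisation analysis among people who had COVID-19 pools illnesses from March 2020 into 2021 with no term or stratum for when the illness occurred.

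*Combined protocol and SAP*

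**What the plan says.** The Study endpoints section relates strategies and combinations of prophylactic drugs, used at any point since March 2020, to "the risk of hospitalization of subjects who had at least one COVID-2019 case". This is the only one of the three drug-strategy endpoints whose wording restricts it to people with COVID-19. The severe-case endpoint uses the same exposure window but does not state its denominator.

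The Statistical analysis plan section says that the relation between subject characteristics and the variables of interest "will be assessed using a one-dimensional and multidimensional (polynomial) logistic regression model for variables" with no more than 20% missing. The final model is the one with the lowest AIC. Crude odds ratios come from 2x2 tables. No covariate is named, none is forced into the model, and no stratification is mentioned.

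The Study variables section covers the illness with one general entry, "Characteristics of the disease case, its treatment". Date of onset, test or admission is not named.

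On the period covered, the justification states that "The first case of COVID-19 in Ukraine was detected in early March, 2020", and the synopsis is version "0.2, 15.02.2021". Data collection then lasts 3 months.

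**The concern.** The cases arise over roughly a year of an epidemic. Two things may change over that time: how many people use a given prophylactic, and how likely a recorded case is to be admitted (for example, if early testing reached mainly sicker people, or if admission practice changed). If both change, onset period is a confounder. A single pooled 2x2 table then mixes the periods, and adjusting for age, comorbidity or employer does not remove the effect. A logistic model chosen only by AIC need not contain a period term even if the date is collected.

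At stake is the odds ratio for hospitalisation, which the plan reports crude and adjusted, with confidence intervals and p-values. A drug without effect could look protective or harmful. This is a different problem from counting use that began after the illness, since it remains when all counted use came first.

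**Working it through.** The plan has no figure to reproduce. The sample size entry reads "Not applicable as it is exhaustive study", and "3443 subjects" is the only count. Numbers of cases, severe cases and admissions are not given. The check therefore asks whether the mechanism works and how large it could be. Every rate below is an assumption.

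**Set-up.** 600 cases, 300 early and 300 late. Use is u1 early and u2 late; admission is h1 early and h2 late. Within each period, admission does not depend on use, so the true odds ratio is 1. The pooled cells are:

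- a (users admitted) = 300 × (u1·h1 + u2·h2)
- b (users not admitted) = 300 × (u1·(1−h1) + u2·(1−h2))
- c (non-users admitted) = 300 × ((1−u1)·h1 + (1−u2)·h2)
- d (non-users not admitted) = 300 × ((1−u1)·(1−h1) + (1−u2)·(1−h2))

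Pooled OR = ad/(bc); 95% CI = exp(ln OR ± 1.96·√(1/a + 1/b + 1/c + 1/d)).

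**One case in full.** Use 20% then 50%, admission 30% then 10%:

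- a = 300 × (0.06 + 0.05) = 33
- b = 300 × (0.14 + 0.45) = 177
- c = 300 × (0.24 + 0.05) = 87
- d = 300 × (0.56 + 0.45) = 303
- OR = (33 × 303)/(177 × 87) = 9999/15399 = 0.65; standard error of ln OR = 0.225; CI 0.42 to 1.01

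**All settings with falling admission.**

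| Use early, late | Admission early, late | Pooled OR (95% CI) |
|---|---|---|
| 20%, 50% | 15%, 10% | 0.86 (0.51 to 1.44) |
| 20%, 50% | 20%, 10% | 0.77 (0.47 to 1.24) |
| 20%, 50% | 30%, 10% | 0.65 (0.42 to 1.01) |
| 10%, 60% | 30%, 10% | 0.47 (0.30 to 0.75) |

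With the admission trend reversed, the four odds ratios become 1.16, 1.29, 1.49 and 1.93. If use or admission is the same in both periods, the pooled odds ratio is 1.00.

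**Other assumptions.** With 35% of cases early, use 20% then 60% and admission 20% then 10%, the pooled odds ratio is 0.73. With 700 cases, the chance of p<0.05 is then about 29%, against a nominal 5%.

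**Effect of stratifying.** For the case worked in full, the early stratum has 18 users admitted, 42 users not admitted, 72 non-users admitted and 168 non-users not admitted. The late stratum has 15, 135, 15 and 135. The Mantel-Haenszel numerator is 18×168/300 + 15×135/300 = 10.08 + 6.75 = 16.83. The denominator is 42×72/300 + 135×15/300 = 16.83. The stratified odds ratio is 1.00.

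**Why use may follow onset date.** If only use before illness counts, a later case has had longer to start. At an assumed constant start rate of 5% per month, 1 − exp(−0.05) = 5% have started by month 1 and 1 − exp(−0.60) = 45% by month 12. This arithmetic does not apply when use at any point up to the questionnaire counts.

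**The case against.** **The stated exposure weakens the link.** A reader might infer that early cases had weeks to start a drug and late cases most of a year, so that use must differ by onset date. The endpoints do not support that. They count use at any point since March 2020, which gives everyone nearly the same look-back whatever the date of illness. Under that definition the bias needs some other reason for use to differ by onset date. The link is direct only if use is counted before illness. The Methodology section has a questionnaire block for cases that collects prophylactics, but does not say whether that means use before illness. This objection stands, and it narrows the point.

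**Severity.** A reader might infer that the severe-case endpoint is also an analysis among cases. Its wording does not say so, and the plan states that all analyses use the whole available population. If people without COVID-19 are in the denominator, they have no onset month and a period term cannot be fitted.

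**Unspecified rather than excluded.** A reader might infer that the plan rules out a time term. It names no covariates at all and defers the main analysis steps to a separate plan that is not supplied. The questionnaire may already hold a date. That is fair. Even so, the pooled table and the AIC-only selection are stated, and neither secures a period term.

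**Descriptive aim.** The plan says "This study is not intended to accept or reject pre-defined hypotheses, thus statistical analysis will mainly be descriptive". It also promises adjusted odds ratios with confidence intervals and p-values, and the stated purpose is to relate prophylactic use to incidence and serious complications. The Study limitations section mentions unequal exposure duration from long data collection and possible inverse relations, but not when the illness occurred.

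**Conclusion.** The point holds for hospitalisation among people who had COVID-19, and for any severity analysis restricted to cases. It is worth changing because the remedy is cheap and the pooled odds ratio can mislead. It does not show that the results will be biased.

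The size is unknown. Under the assumed falling-admission settings the pooled odds ratio lies between 0.86 and 0.47, and only the most extreme setting (use 10% then 60%, admission 30% then 10%) gives an interval that excludes 1. A reader might infer that a spurious protective effect is likely. The documents do not support that: they give no trend in use, testing or admission, the bias could run either way, and it is absent if use or admission risk is constant over time.

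**What to change.** - Record the month of onset, or of the positive test, in the questionnaire block for cases, if it is not already there.
- For hospitalisation, and for severity among cases, keep a coarse onset period in the logistic model outside AIC selection. Two or three epidemic periods would do. Calendar quarters cost 4 degrees of freedom from March 2020 to the first quarter of 2021, and 5 if collection reaches the second quarter.
- Report a Mantel-Haenszel odds ratio stratified by that period beside, or instead of, the pooled 2x2 odds ratio.
- Where a subject had several cases, use the admitted case, or the first if none was admitted.
- Put antibody-only or undated cases in an unknown category, at one further degree of freedom. None is then dropped, and the 20% missing-data rule does not remove the variable.
- State the denominator of the severe-case model. Do not apply the term where it includes people without COVID-19.

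The cost is one field, a few sentences in the analysis plan, some recall error in the month, and slightly wider intervals. Confounding by period can remain within the unknown category. If collection has closed without any date, the limitation should be stated in the report.

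### The 20% missingness rule, with no imputation, lets completeness rather than confounding decide which variables are adjusted for and which subjects are analysed

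*Combined protocol and SAP*

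**What the plan says.** All the rules at issue are in the statistical analysis plan section of the combined document.

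- **Entry to the models:** a one-dimensional and multidimensional "logistic regression model for variables, which have no more than 20% omitted data".
- **Missing values:** "No conditional calculation methods will be applied to the missed values".
- **Analysis set:** "All types of analysis will be done for the entire available study population with available data".
- **Selection:** "The final model will be selected with a view to minimizing the Akaike information criterion value".
- **Output:** "Rough odds ratios and adjusted odds ratios with corresponding 95% confidence intervals and p-values will be generated".

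No confounder is named as mandatory. The section plans no sensitivity analysis for missing data and no comparison of included with excluded subjects.

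Two other sections bear on how much may be missing. Under Methodology, the electronic form cannot be closed with a required field blank, and designated staff at each organisation check completeness; which fields are required is not stated. Under Study limitations, the plan expects gaps ("There may be difficulties in filling in the missing data") and lists the absence of verification and queries as a source of distortion.

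**The concern.** The study's purpose is the relationship between prophylactic use and COVID-19. Use was not randomised, so the answer rests on the adjusted odds ratios, and these depend on which variables are adjusted for and which subjects remain.

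The 20% rule judges a variable by its completeness and ignores its role. A strong confounder with 21% missing is left out, while a weak one with 19% missing may enter. Without imputation, each variable that enters removes every subject who lacks it, and the losses add up across variables.

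AIC selection adds two difficulties. It can drop a confounder that is fully observed. Also, AIC values are comparable only between models fitted to the same subjects, and candidates with different incomplete covariates would be fitted to different subsets.

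At stake are residual confounding in the main estimates and a loss of the precision that an exhaustive survey should give.

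**Working it through.** **Inputs from the documents.** The Number of subjects row gives "3443 subjects". The 20% limit and the missing-value rule are quoted above. There is no sample size or power figure to reproduce, since that row reads "Not applicable as it is exhaustive study".

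**Inputs assumed.** The number of covariates (k = 8), the share missing in each (m), the pattern of overlap, and all confounder strengths. None of these is in the documents.

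**Step 1: subjects left in a multivariable model.**

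- Gaps all in the same subjects: 3443 × (1 − m)
- Independent gaps: 3443 × (1 − m)^8
- Gaps overlapping as little as possible: 3443 × max(0, 1 − 8m)
- Standard error factor: 1/√(fraction retained), treating the lost subjects as a random subset

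| Missing per covariate | Same subjects | Independent | Least overlap |
|---|---|---|---|
| 1% | 3409 (SE ×1.01) | 3177 (SE ×1.04) | 3168 (SE ×1.04) |
| 5% | 3271 (SE ×1.03) | 2284 (SE ×1.23) | 2066 (SE ×1.29) |
| 10% | 3099 (SE ×1.05) | 1482 (SE ×1.52) | 689 (SE ×2.24) |
| 20% | 2754 (SE ×1.12) | 578 (SE ×2.44) | 0 |

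For example, 0.95^8 = 0.663, 0.663 × 3443 ≈ 2284, and 1/√0.663 = 1.23. Every row satisfies the 20% rule.

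**Step 2: a confounder left out when the true exposure odds ratio is 1.00.**

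*Set A.* Prevalence 25%; odds ratio 2.5 with COVID-19 (baseline risk 15%) and 3 with prophylactic use (baseline use 40%).

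- Risk with the confounder: odds 0.1765 × 2.5 = 0.4412, risk 0.306. Use with the confounder: odds 0.667 × 3 = 2, use 0.667.
- Confounder prevalence in users: 0.25 × 0.667 / (0.25 × 0.667 + 0.75 × 0.40) = 0.357. In non-users: 0.25 × 0.333 / (0.25 × 0.333 + 0.75 × 0.60) = 0.156.
- Risk in users: 0.357 × 0.306 + 0.643 × 0.150 = 0.2058. In non-users: 0.156 × 0.306 + 0.844 × 0.150 = 0.1744.
- Crude odds ratio: (0.2058/0.7942) / (0.1744/0.8256) = 1.23.

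*Set B.* Baseline risk 20%; confounder odds ratio 2 (risk 0.333); prevalence 40% in users and 20% in non-users.

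- Risks: 0.4 × 0.333 + 0.6 × 0.2 = 0.2533 and 0.2 × 0.333 + 0.8 × 0.2 = 0.2267.
- Crude odds ratio: (0.2533/0.7467) / (0.2267/0.7733) = 1.16. With the prevalences reversed it is 0.86.

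The bias can therefore run either way, including towards apparent protection. A weaker confounder does less: with odds ratio 1.5 in Set B, the figures are 1.09 and 0.92.

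**Step 3: AIC across different subsets.** The log-likelihood is a sum over subjects. At an assumed 20% risk, a null model contributes −2(0.2 ln 0.2 + 0.8 ln 0.8) = 1.00 per subject on average. Losing 5% of 3443, about 172 subjects, lowers AIC by about 172 whatever the fit, against a penalty of 2 per parameter. Unless the set is held fixed, minimising AIC favours incomplete covariates.

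**The case against.** The strongest reply is that little may be missing. Required fields block an unfinished form and completeness is checked on site. If that holds missingness to 1%, eight covariates still leave about 3177 subjects. The 578 figure needs all eight at the limit at once with independent gaps. This stands: the loss could be trivial, and the documents do not settle it. Yet the plan expects gaps and sets a rule for them, so the rule should work when it is needed.

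Three further replies have some force.

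- **Complete-case analysis is never written.** It is inferred from the no-imputation sentence, itself a reading of a translated phrase, and from how standard logistic software works. Details are also deferred to a separate plan. Even so, both rules are fixed here, and a later document consistent with them inherits the problem.
- **Complete-case logistic regression need not be biased.** If missingness does not depend on the outcome given the covariates, the odds ratios remain valid and only precision is lost. The plan includes nothing that would check this.
- **The analysis is mainly descriptive.** It is, but adjusted odds ratios with intervals and p-values are still promised.

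A reader might also infer that severity and hospitalisation fail the 20% rule because they are blank for non-cases. The documents do not support this. Case questions form a separate block for those who had COVID-19, the hospitalisation endpoint is defined among cases, analyses use available data, and subpopulation analyses are provided for. A question never put to a subject is not naturally omitted data.

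**Conclusion.** The concern holds as a matter of stated rules. A confounder can be excluded for incompleteness alone, and the limit per variable does not bound the cumulative loss of subjects. This should be changed before analysis.

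Its size cannot be determined from the documents. With 8 covariates assumed, the retained number runs from about 3177 (1% missing each, independent) to 578 (20%, independent), with 2754 if the 20% gaps coincide. The 0.86-1.23 range for a dropped confounder illustrates the strengths assumed. It applies only if such a confounder exceeds 20% missing, and no listed variable can be shown to do so.

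A reader might infer that the study will lose most of its subjects, that its estimates will be biased in a known direction, or that severe and hospitalised outcomes will suffer most. The documents give no missingness rates or outcome frequencies to support any of these.

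**What to change.** 1. **Name the confounders in advance.** Draw them from the Study variables list, for example age, gender, weight and height, household size, lifestyle and comorbidities, and add organisation. Keep the set in every adjusted model regardless of the 20% rule and of AIC.
2. **Replace the no-imputation sentence.** Multiply impute missing covariates, with an imputation model containing outcome, exposure, all covariates and organisation, and pool by Rubin's rules. Do not impute questions that were not put to a subject.
3. **Report alongside it** the complete-case result, the missing share of each variable and the N of each model.
4. **Limit AIC to optional terms**, comparing candidates on one common set of subjects. Rubin's rules pool estimates and do not give a single AIC, so the plan should state which set is used.

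The cost is new wording and some programming, with no new data. The downside is reliance on missing-at-random, which is open to doubt for recalled self-report when much is missing. The complete-case comparison is the check on it. If missingness proves to be about 1%, the two results should nearly agree and little effort will have been spent.
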